7.2.1 Surgical Adverse Event Grading

Anticipated Adverse Effects

Complications related to the surgical procedure will be documented. ‘Minor’ are those defined as leading to little or no effect on function, and not resulting in a significant increase in hospital stay. ‘Major’ complications are those resulting in permanent sequelae with functional limitations, or those leading to a significant increase in hospital stay. Surgical adverse events that cannot be graded by CTCAE terminology (e.g., prolonged intubation) will be reviewed on a weekly basis by the Investigator and by the Data and Safety Monitoring Committee (DSMC) per their established reviewing schedule. All other events that can be graded by CTCAE terminology will use the CTCAE grading. This includes wound infections, hemorrhage, cerebral spinal fluid (CSF) leak, and respiratory and neurologic adverse events.

7.3 **Adverse Event Reporting**

All Adverse Events (AEs) will be entered into OnCore®. Appendix D includes detailed information about PNOC reporting timelines.

The study period during which AEs and SAEs must be reported begins after informed consent is obtained and ends 30 days following the last administration of study treatment. After this period, only SAEs that are attributable to study treatment should be reported. Subjects removed from therapy for unacceptable adverse event(s) will be followed until adverse event(s) resolves or returns to baseline status.

The PNOC Investigator will assign attribution of the possible association of the event with use of the study therapy, and this information will be entered into OnCore®. The Investigator must also comply with all reporting requirements to their institutional Data and Safety Monitoring Committee (DSMC) and Institutional Review Board (IRB).

7.4 **Serious Adverse Events and Expedited Reporting**

All Adverse Events which meet the definition of ‘Serious’ as well as other medically significant events described below require expedited reporting to PNOC. Below are instructions for recording and reporting of these events. Please contact the PNOC Operations Office [REDACTED] with any questions regarding expedited reporting requirements for this study. See 7.1.3 for the definition of an SAE.

All SAEs (see above definition) on any PNOC trial, regardless of relationship, must be reported to PNOC via OnCore and Email within one business day of first PI awareness, even if the SAE is ongoing. The SAE must be followed until resolution:

- **OnCore:** All SAEs must be entered into the Subject Console in OnCore (<https://oncore.ucsf.edu/> > Subject Console > SAE Tab on left). The OnCore SAE record should be updated immediately as new information becomes available until the SAE is resolved. (Toxicity segment MUST be completed. Don’t forget to click “Add” button.) Please refer to the “PNOC OnCore SAE Entry Guide: Field by Field” for more information.
- **Email:** Please also email [REDACTED] with, at minimum, the following information:
In the subject line: “SAE: Subject PNOC ID” (e.g. “SAE: PNOCxxx-1”)
In the body of the email: Subject PNOC ID and the OnCore assigned SAE number
- **Site IRB:** Each PNOC site is also responsible for following their own IRB guidelines for reporting SAEs.

SAE Data Entry in AE CRF:

All SAEs must also be entered into the AE CRF for that Cycle (Subject Console > Forms by Status/Forms by Visit). This entry must take place within 10 days of the last day of the Cycle in which the SAE occurred, or as soon as possible in the case of an SAE that was discovered late. Please reference the “PNOC OnCore SAE Reporting and Entry” in SharePoint for more information.

SAE Deviations:

If the protocol procedures around SAEs are not followed (e.g. reporting timelines or dose modifications), a Deviation may also need to be entered in OnCore (Subject Console > Deviation Tab on left). Please reference the “PNOC Deviation Reporting Guidelines” in SharePoint for more information.

7.4.1 **Medically Significant Events**

Email notification to PNOC Operations Office [REDACTED] **within one business day** of first PI awareness:

- Reports of pregnancy exposure (pregnancy encompasses the entire cycle of pregnancy and delivery, perinatal and neonatal outcomes, even if there were no abnormal findings; both maternal and paternal exposure is collected)
- Reports of lactation exposure

- Overdose (with or without an SAE)
- Abuse (use for non-clinical reasons with or without an SAE)
- Inadvertent or accidental exposure

7.4.2 **PNOC Reporting to the UCSF Data and Safety Monitoring Committee**

If a death occurs during the treatment phase of the study, or within 30 days after the last administration of the study drug(s), and is determined to be related either to the investigational drug or to any research related procedure, the Study Chair and the PNOC Operations Office must be notified by the member institution **within 1 business day**. The Study Chair or the PNOC Operations Office must then notify the UCSF DSMC Chair, or qualified alternate, within 1 business day of this notification. The contact may be by phone or e-mail. Each participating site will follow their institutional reporting guidelines to institutional DSMC.

7.4.3 **PNOC Reporting to UCSF Institutional Review Board (IRB)**

The PNOC Operations Office must report events meeting the UCSF IRB definition of “Unanticipated Problem” (UP) **within 10 business days** of awareness of the event.

Each participating site will follow their institutional reporting guidelines to the IRB.

7.4.4 **PNOC Reporting to the Food and Drug Administration (FDA)**

If the study is being conducted under an IND, the PNOC Operations Office is responsible for determining whether or not the suspected adverse reaction meets the criteria for expedited reporting in accordance with Federal Regulations (21 CFR §312.32).

The PNOC Operations Office must report in an IND safety report any suspected adverse reaction that is both serious and unexpected. The Sponsor-Investigator (PNOC) needs to ensure that the event meets all three definitions:

- Suspected adverse reaction
- Unexpected
- Serious

If the adverse event does not meet all three of the definitions, it should not be submitted as an expedited IND safety report.

The timeline for submitting an IND safety report to FDA is no later than **15 calendar days** after the PNOC Operations Office determines that the suspected adverse reaction qualifies for reporting (21 CFR 312.32(c)(1)).

Any unexpected fatal or life-threatening suspected adverse reaction will be reported to FDA no later than **7 calendar days** after PNOC initial receipt of the information (21 CFR 312.32(c)(2)).

Any relevant additional information that pertains to a previously submitted IND safety report will be submitted to FDA as a Follow-up IND Safety Report without delay, as

soon as the information is available (21 CFR 312.32(d)(2)).

7.4.5 **PNOC Reporting to Midatech Pharma (supplier of MTX110 injection)**

The Sponsor-Investigator (PNOC) is responsible for reporting of serious adverse events to Midatech Pharma. SAEs should be reported to the Chief Medical Officer at Midatech Pharma [REDACTED] within one business day using the same criteria described in Section 7.4.3 PNOC Reporting to the UCSF Data and Safety Monitoring Committee. Additionally, copies of all PNOC safety reports to the FDA and any related correspondence should be simultaneously copied to Midatech.

Periodic safety reports with tabulation of all AEs and SAEs should be provided to Midatech every 3 months during the study.

7.5 **Secondary Malignancy**

A *secondary malignancy* is a cancer caused by treatment for a previous malignancy (*e.g.*, treatment with investigational agent/intervention, radiation or chemotherapy). A secondary malignancy is not considered a metastasis of the initial neoplasm.

- Leukemia secondary to oncology chemotherapy (*e.g.*, acute myelocytic leukemia [AML])
- Myelodysplastic syndrome (MDS)
- Treatment-related secondary malignancy

Any malignancy possibly related to cancer treatment (including AML/MDS) should also be reported via the routine reporting mechanisms outlined in each protocol.

8. PHARMACEUTICAL INFORMATION

8.1 **Study Agent**

8.1.1 **MTX110 injection**

Product description: MTX110 is the study agent supplied by Midatech Pharma. The drug is a formulation of liquid panobinostat. This agent is not FDA approved for the treatment of primary CNS brain tumors or brainstem glioma (DIPG).

How the drug is supplied: The product is presented 10 ml amber glass vials at a concentration of 40 μ M (13.98 μ g/ml).

Storage and handling: The product is shipped under refrigerated conditions (2°C to 8°C). On receipt at the pharmacy, the product should be removed for the shipping package and stored at refrigerated conditions (2°C to 8°C) prior to reconstitution for use.

Ordering: Pharmacy will order directly from Midatech Pharma.

Stability: When stored in vials at 5°C the product remains stable for at least 42 days. Once reconstituted the product should be used within 24 hours.

Route of administration: Intratumoral infusion via convection enhanced delivery (CED). See Section 5.0 for specific details.

Accountability: The investigator, or a responsible party designated by the investigator, will be responsible for drug accountability and this will be managed per each PNOC institution guidelines.

9. EVALUATION CRITERIA

Although response is not the primary endpoint of this trial, subjects with measurable disease will be assessed by standard imaging criteria.

9.1 Response Criteria

9.1.1 Definitions

Evaluable for toxicity. All subjects will be evaluable for toxicity from the time of their first treatment with MTX110 injection.

Evaluable for objective response. Only those subjects who have measurable disease present at baseline, have received at least one cycle of therapy, and have had their disease re-evaluated will be considered evaluable for response. These subjects will have their response classified according to the definitions stated below. (Note: Subjects who exhibit objective disease progression prior to the end of cycle 1 will also be considered evaluable.)

Evaluable Non-Target Disease Response. Subjects who have lesions present at baseline that are evaluable but do not meet the definitions of measurable disease, have received at least one cycle of therapy, and have had their disease re-evaluated will be considered evaluable for non-target disease. The response assessment is based on the presence, absence, or unequivocal progression of the lesions.

9.1.2 Disease Parameters

Measurable disease

Measurable disease is defined as lesions that can be accurately measured in two dimensions (longest diameter to be recorded) with a minimum size of no less than double the slice thickness.

All tumor measurements will be recorded in millimeters or decimal fractions of centimeters. Previously irradiated lesions are considered non-measurable except in cases of documented progression of the lesion since the completion of radiation therapy.

All measurements will be taken using a ruler or calipers. All baseline evaluations will be performed as closely as possible to the beginning of treatment and never more than 30 days before the beginning of the treatment.

The same method of assessment and the same technique will be used to characterize each identified and reported lesion at baseline and during follow-up.

Non-measurable disease

Non-measurable disease is all other lesions (or sites of disease), including small lesions (< double the slice thickness).

Target and Non-target lesion

Tumor dimensions are determined by measurement of the longest tumor dimension and its perpendicular for each target lesion. For most CNS tumors, only one lesion/mass is present and therefore is considered a “target” for measurement/follow up to assess for tumor progression/response. If multiple measurable lesions are present, up to 3 can be selected as “target” lesions. Target lesions should be selected on the basis of size and suitability for accurate repeated measurements. All other lesions will be followed as non-target lesions (including CSF positive for tumor cells). The lower size limit of the target lesion(s) should be at least twice the thickness of the slices showing the tumor to decrease the partial volume effect.

Tumor Measurements

Regarding MRI imaging, the sequence that best highlights the tumor (T1 enhanced or T2 weighted or FLAIR images) will be chosen to determine response criteria. The same sequence should be used for serial measurements. Response determination will be based on a comparison of an area [W (longest diameter of the target lesion) \times T (transverse measurement, perpendicular to W)] between the baseline assessment and the study date designated in the follow-up Report Form. Reports for the follow-up exams should reiterate the measurements obtained at baseline for each target lesion. Nontarget lesions or newly occurring lesions should also be enumerated in these reports, and changes in non-target lesions should be described.

1. For MRI imaging, the longest diameter can be measured from the axial plane or the plane in which the tumor is best seen or measured. The longest measurement of the tumor is referred to as the width (W).
2. The perpendicular measurements should be determined - transverse (T) measurement, perpendicular to the width in the selected plane.
3. The cystic or necrotic components of a tumor are not considered in tumor measurements. Therefore only the solid component of cystic/necrotic tumors should be measured. If cysts/necrosis composes the majority of the lesion, the lesion may not be “measurable”.

Options:

- If the cyst/necrosis is eccentric, the W and T of the solid portion should be measured, the cyst/necrosis will be excluded from measurement
- If the cyst/necrosis is central but represents a small portion of the tumor (< 25%), disregard and measure the whole lesion
- If the cyst/necrosis is central but represents a large portion of the tumor, identify a solid aspect of the mass that can be reproducibly measured
- Leptomeningeal tumor spread is usually not a target lesion, and usually cannot be measured accurately. Presence and location of leptomeningeal tumor spread should be noted and change in extent/thickness assessed on follow up studies.

Overall Response Assessment:

The overall response assessment takes into account response in both the target and non-target lesion, and the appearance of new lesions, where applicable, according to the criteria described in the table below. The best overall response is the best response recorded from the start of the treatment until disease progression/recurrence (taking as reference for progressive disease the smallest measurements recorded since the treatment started). The subject's best response assignment will depend on the achievement of both measurement and confirmation criteria.

Target Lesion(s)	Non Target Lesion (s)	New Lesions	Overall Response	Best Response for this Category Also Requires
CR	CR	No	CR	> 8 weeks confirmation
CR	IR/SD	No	PR	> 8 weeks confirmation
PR	CR/IR/SD	No	PR	
SD	CR/IR/SD	No	SD	documented at least > 4 weeks from baseline
PD	Any	Yes or No	PD	
Any	PD	Yes or No	PD	
Any	Any	Yes	PD	

CR – Complete Response; PR – Partial Response; SD – Stable Disease; PD – Progressive Disease; IR – Incomplete Response

Response Criteria for Target/Non-Target Lesions:

Response criteria are assessed in 2 dimensions – the product of W x T. To assess response/progression, the ratio is calculated: **W x T (current scan) divided by W x T (reference scan)**. Development of new disease or progression in any established lesions is considered progressive disease, regardless of response in other lesions – e.g. when multiple lesions show opposite responses, the progressive disease takes precedence.

For purposes of this study, response criteria for target lesions are:

Complete Response (CR): Complete disappearance of all known disease for at least 8 weeks. Complete response is dated from the time all lesions have disappeared on a stable or decreasing dose of corticosteroids.

Partial response (PR): A reduction of at least 50% in the size of all measurable tumors

as quantitated by the sum of the products of the largest diameters of measurable lesions and maintained for at least 8 weeks on a stable or decreasing dose of corticosteroids. Partial response is dated from the time of first observation. In addition, there can be no appearance of new lesions or progression of any lesion.

Stable Disease (SD): A decrease of <50% or an increase of <25% in the sum of the products of the largest diameters of measurable lesions and no evidence of new lesions for at least 4 weeks on a stable or decreasing dose of corticosteroids.

Progressive Disease (PD): $\geq 25\%$ increase in the sum of the products of the largest diameters of the measurable lesions or the appearance of one or more new lesions.

9.1.3 Duration of Response

Duration of overall response: The duration of overall response is measured from the time measurement criteria are met for CR or PR (whichever is first recorded) until the first date that recurrent or progressive disease is objectively documented (taking as reference for progressive disease the smallest measurements recorded since the treatment started).

The duration of overall CR is measured from the time measurement criteria are first met for CR until the first date that progressive disease is objectively documented.

Duration of stable disease: Stable disease is measured from the start of the CED infusion treatment until the criteria for progression are met, taking as reference the smallest measurements recorded since the treatment started, including the baseline measurements.

9.1.4 Progression-Free Survival

PFS is defined as the duration of time from diagnosis to time of progression or death, whichever occurs first.

9.1.5 Overall survival

OS is defined as the duration of time from diagnosis to time of death.

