Duration of Therapy	Eligible subjects will receive MTX110 after completion of standard focal radiotherapy (minimum of 28 days, maximum of 14 weeks from radiation therapy). Treatment will occur every 4-8 weeks. Treatment will continue for up to 24 months or until tumor progression or intolerable toxicity. If subjects continue to derive clinical benefit, discussion with investigators and study sponsor will determine feasibility and clinical appropriateness to continue therapy beyond 24 months.
Duration of Follow up	All subjects will be followed for safety, time to tumor progression and overall survival.
Duration of study	The study will reach completion approximately 3 years from the time the study opens to accrual.
Study Drugs	MTX110 is a water soluble formulation of panobinostat, administered via CED; concentration of gadoteridol (ProHance) will be 0.5 mM in all dose levels; both agents will be combined and co-infused via the same catheters.

Safety Assessments
	
We will use CTCAE version 4.0 for adverse event reporting; surgical complications will be graded as outlined in the protocol. Subjects will undergo clinical evaluation and brain MR imaging prior to any CED to assess for related toxicity, as well as tumor status. Toxicity is defined per standard pediatric phase I guidelines including interruption of planned therapy > 10 weeks to allow for recovery from toxicity of prior CED MTX110 injection.

Efficacy Assessments
	
We will assess the preliminary efficacy using overall survival at 12 months (OS12) in 19 evaluable DIPG patients treated within the expansion cohort which will include subjects treated as part of the dose escalation portion of the trial on the recommended phase 2 dose (RP2D). The most recent Children’s Oncology Group study that treated children newly diagnosed with DIPG with a combination of radiation therapy and temozolomide resulted in an OS12 rate of 40% (SD ± 6.5%). A sample size of 19 patients achieves 80% power to detect a difference of 30% using a one sided exact binominal test. The target significance level is 5% and the actual significance level is 3.5% with this test. If 12 or more patients are alive at 12 months, the null hypothesis that OS12 is 40% will be rejected.

Unique Aspects of this Study
	
This is the first study to evaluate the safety and preliminary efficacy of the use of repeated CED of MTX110 with real time gadoteridol imaging in children with DIPG.

EXPERIMENTAL DESIGN SCHEMA

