3.3 Inclusion Criteria

Patients must have eligibility evaluations performed within 14 days prior to registration (unless otherwise stated) and must meet all inclusion and none of the exclusion criteria. In addition, the patient must be thoroughly informed about all aspects of the study, including the study visit schedule, required evaluations and all regulatory requirements. The written informed consent must be obtained from the patient or their legal guardian prior to enrollment. The following criteria apply to all patients enrolled onto the study unless otherwise specified. Tumor biopsy is not required prior to enrollment on study, unless imaging characteristics are not consistent with DIPG diagnosis and as detailed in 3.2.1. The Inclusion Criteria will be applied **after** patients have completed radiotherapy and within the given time frame per observation as listed below. Enrollment into the trial occurs after completion of radiation therapy and if all eligibility criteria are met.

- 3.3.1 Patients with newly diagnosed DIPG by MRI; defined as patients with a pontine location and diffuse involvement of at least 2/3 of the pons are eligible without histologic diagnosis. For lesions with typical imaging features, biopsy is **neither encouraged nor required for eligibility**. Tumors that are biopsied will be eligible if proven to be supportive of the diagnosis of a DIPG. Consensus of diagnosis by the study team must be met.
- 3.3.2 Patients who have completed focal radiotherapy within 14 weeks from time of enrollment are eligible.
- 3.3.3 Treatment must begin at a minimum of 4 weeks after, but no later than 14 weeks after, the date of completion of focal radiotherapy.
- 3.3.4 Prior Chemotherapy: Patients should be at least 30 days from last chemotherapy dose prior to start of CED infusion, with exception of antibody half-lives. For antibody therapies, at least 3 half-lives of the antibody after last dose of monoclonal antibody should have passed prior to CED infusion. Patients less than 30 days from last chemotherapy dose should be discussed with the study chair(s).
- 3.3.5 Prior Radiation: Patients must have received prior treatment with standard focal radiotherapy as part of initial treatment for DIPG and had their last dose at least 4 weeks prior to and no later than 14 weeks from the first CED treatment. Patients beyond 14 weeks from radiation therapy but with stable disease should be discussed with the study chair.

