10.3 Sample Size and Accrual

The number of subjects enrolled in the safety study will depend upon the DLTs observed and the number of dose levels tested as the study progresses in accordance with an ATD followed by a 3+3 design. The ATD is expected to enroll 1 to 7 subjects with a minimum of 5 subjects in the 3+3 design. Additional subjects may be enrolled depending on the dose de-escalations, expansion of dose exploration, or exploration of intermediate doses that occur. Once these dose levels have been assessed, a detailed review of the safety and efficacy data will be performed and discussed with the FDA and the DSMC to discuss either further dose escalation or enrollment into the efficacy study.

Secondary Objective: The most recent Children’s Oncology Group study that treated children newly diagnosed with DIPG with a combination of radiation therapy and temozolomide resulted in an OS12 rate of 40% (SD ± 6.5%). A sample size of 19 patients achieves 80% power to detect a difference of 30% using a one sided exact binominal test. The target significance level is 5% and the actual significance level is 3.5% with this test. If 12 or more patients are alive at 12 months, the null hypothesis that OS12 is 40% will be rejected.

Stopping Rules:

Both the ATD and 3+3 have inherent stopping rules; however, it should be noted that this study will be stopped for further review by the DSMC and study team as well as FDA by:

- The occurrence of 1 or more irreversible neurological deficits that are grade 3 or higher and definitely related to the procedure based on evidence on MRI such as intraparenchymal hemorrhage, worsening edema or necrosis.

- If more than 20% of subjects develop significant, irreversible deterioration during the infusion.
- If more than 20% of subjects do not get study drug infused due to surgical complications during the catheter placement.

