10.5 Analysis of Endpoints

Intent-to-Treat Population (ITT): The ITT population will include all subjects who are enrolled in the study. The ITT population will be the primary population for evaluating efficacy and subject characteristics.

As-Treated Population (AT): The AT population will include all subjects who receive at least 1 dose of study drug. The AT population will be the primary population for evaluating safety.

Analysis of Primary Endpoint

- Safety of repeated CED of MTX110 following standard of care focal radiotherapy will be assessed by monitoring for adverse events, scheduled laboratory assessments, vital sign measurements, and physical examinations for subjects who receive the drug. The severity of toxicities will be graded according to the NCI CTCAE v4.0. Adverse events and clinically significant laboratory abnormalities (meeting Grade 3, 4, or 5 criteria according to CTCAE) will be summarized by maximum intensity and relationship to study drug(s). Grade 1 and 2 adverse events will be summarized if related to study therapy. Descriptive statistics will be utilized to display the data on toxicity.

Analysis of Secondary Endpoint

- We will assess the preliminary efficacy using overall survival at 12 months (OS12) in 19 evaluable DIPG patients treated within the expansion cohort which will include subjects treated as part of the dose escalation portion of the trial on the recommended phase 2 dose (RP2D). Analyses will be performed after all enrolled subjects have completed 12 months, or whenever the status of all subjects has been established, whichever comes first. The primary analysis will be based on the Kaplan-Meier method. Kaplan-Meier estimates and the associated 95% CIs will be calculated for OS12. As described above, if 12 or more of the 19 patients are alive at 12 months, the null hypothesis that OS12 is 40% will be rejected.

Analysis of Exploratory endpoint

The exploratory aims associated with this study will be descriptive and will be limited to frequency tables and summary statistics.

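### OS12 is counted from diagnosis, but children enter only after radiotherapy, so the 3.5% level of 12 of 19 holds only if the 40% benchmark was selected in the same way

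*Combined protocol and SAP*

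**What the plan says.** All references are to the combined protocol and SAP.

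- **Time origin.** Section 9.1.5: "OS is defined as the duration of time from diagnosis to time of death". Sections 10.1, 10.3 and 10.5 use OS12 without giving another origin.
- **Entry.** Section 3.3: "Enrollment into the trial occurs after completion of radiation therapy and if all eligibility criteria are met". Enrolment may fall up to 14 weeks after radiotherapy (3.3.2). First convection-enhanced delivery (CED) comes 4 to 14 weeks after it (3.3.3), with later entry open to discussion for children with stable disease (3.3.5). Life expectancy must exceed 12 weeks from the end of radiotherapy (3.3.8), and progression after radiotherapy excludes a child (3.4.1).
- **Null.** Section 10.3 takes it from a cooperative-group study in children "newly diagnosed with DIPG with a combination of radiation therapy and temozolomide resulted in an OS12 rate of 40% (SD ± 6.5" percent). The synopsis repeats this. Neither place gives that study's time origin or entry criteria.
- **Rule.** "If 12 or more patients are alive at 12 months, the null hypothesis that OS12 is 40% will be rejected" (10.3), with the statement "The target significance level is 5% and the actual significance level is 3.5% with this test". Stated power is 80% for a 30-point difference with 19 patients.
- **Analysis.** Section 10.5: "Kaplan-Meier estimates and the associated 95% CIs will be calculated for OS12". On the population, the section says "The ITT population will be the primary population for evaluating efficacy and subject characteristics", where ITT is everyone enrolled, but it also describes the OS12 set as "19 evaluable DIPG patients treated within the expansion cohort". No landmark or delayed-entry adjustment is mentioned.

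**The concern.** The time between diagnosis and entry counts towards each child's 12 months, yet nobody in the trial can die during it. A child who dies during radiotherapy, or who progresses soon after it, never appears in the denominator. The treatment described for the benchmark includes radiotherapy. This suggests, without proving, that those children were counted from before radiotherapy ended, so that early deaths are inside the 40%.

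If so, the trial compares a group selected for having survived to entry with one that was not, and 12 of 19 would be reached more often under an inactive drug than the plan states. Part of an apparent benefit could come from the entry rules. OS12 is a secondary and preliminary endpoint, but it carries the trial's only formal hypothesis test and sets the sample of 19.

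**Working it through.** **Inputs from the documents.** N = 19, cut-off 12, null 0.40, alternative 0.40 + 0.30 = 0.70, one-sided exact binomial test (section 10.3); origin at diagnosis (9.1.5); entry after radiotherapy (3.3).

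**Input not in the documents.** S(entry), the share of benchmark-type children still alive at this trial's entry point. Time from diagnosis to the end of radiotherapy is not given either, so S(entry) cannot be derived. It is varied from 0.98 to 0.80 for illustration.

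**Step 1: reproduce the plan.**
- Level: P(X ≥ 12 | n = 19, p = 0.40) = 0.0352, the stated 3.5%.
- Power: P(X ≥ 12 | n = 19, p = 0.70) = 0.818, against the stated 80%.

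The arithmetic is right for a true null of exactly 40%.

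**Step 2: the null among children who can enter.** Suppose the 40% runs from diagnosis and was not conditioned on reaching entry. Then, for a child alive at entry and an inactive treatment,

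P(alive at 12 months | alive at entry) = S(12)/S(entry) = 0.40/S(entry).

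This exceeds 0.40 whenever any benchmark child dies before the entry point.

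**Step 3: level of the unchanged rule, and the cut-off needed to keep 5%.**

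| S(entry) | Null = 0.40/S(entry) | Level of 12 of 19 | Smallest cut-off with level ≤ 5% | Level at that cut-off |
|---|---|---|---|---|
| 1.00 | 0.400 | 3.5% | 12 | 3.5% |
| 0.98 | 0.408 | 4.1% | 12 | 4.1% |
| 0.95 | 0.421 | 5.3% | 13 | 1.9% |
| 0.90 | 0.444 | 8.0% | 13 | 3.1% |
| 0.85 | 0.471 | 12.0% | 14 | 1.7% |
| 0.80 | 0.500 | 18.0% | 14 | 3.2% |

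**Step 4: where the 5% target is passed.** P(X ≥ 12 | 19, p) = 0.05 at p = 0.4181. Then S(entry) = 0.40/0.4181 = 0.957, so the target is passed once more than about 4.3% would die before entry.

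**Step 5: price of a higher cut-off.** Power at the plan's 70% is 82% for cut-off 12, 67% for 13 and 47% for 14.

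The table conditions on survival to entry only. Excluding children who progressed probably raises the null further, by an amount the documents do not allow one to compute.

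**The case against.** The strongest reply is that the benchmark study is not available here. It may have used the same origin and a comparable post-radiotherapy selection, in which case 3.5% stands. That is right, and it is why the point is conditional. The formula needs two things at once: that the 40% runs from diagnosis, and that it was not conditioned on reaching the same point.

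Nor can the net shift be signed once other differences are let in. The benchmark treatment included temozolomide, this trial admits performance scores down to 50 (3.3.7), and the benchmark's own criteria are unknown. Selection taken alone pushes the null upward; the total of all differences could go either way.

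A reader might infer that the 3.5% is miscalculated, or that a false-positive rate above 5% has been shown. The documents support neither. The figure reproduces, and if early deaths are rare the level stays under 5% (4.1% at 98% surviving to entry).

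A reader might also infer that the 12-of-19 rule should be struck out. The documents do not require that. Section 10.1 calls efficacy a preliminary estimate, section 10.5 already plans a confidence interval, and no go/no-go action is tied to the count. Removing the rule over an unverified mismatch would be a matter of preference.

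What remains is that the plan states a level and a firm rejection rule without the information needed to know whether the level applies, and its analysis does nothing about survival guaranteed up to entry.

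**Conclusion.** The concern holds in conditional form. The mismatch between a clock starting at diagnosis and entry after radiotherapy is in the text. Its effect on the test depends on the unstated origin and selection of the benchmark. If the 40% is an unselected rate from diagnosis, and other things are equal, the level is above 3.5%: 4.1% to 18.0% for 98% down to 80% surviving to entry. The size is illustrative, because S(entry) is not in the documents. The 3.5% and 80% should be read as nominal until the benchmark is described. This should be settled before the readout, since a change made afterwards would look driven by the result.

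**What to change.** Amend the synopsis (Efficacy Assessments) and sections 10.3 and 10.5 before the readout.

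1. State the benchmark's time origin and eligibility. Say that 3.5% and 80% hold only if the 40% applies to children alive and progression-free after radiotherapy.
2. Beside the planned 12-of-19 result, estimate OS12 from diagnosis by Kaplan-Meier with delayed entry, and give its 95% CI. Each child joins the risk set at enrolment, or at first CED if the treated set is analysed; section 10.5 should say which. Interpret any rejection in that light.
3. If a benchmark conditional on the same post-radiotherapy landmark can be obtained, make it the null, recompute the cut-off for 19 and restate level and power.

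**Cost.** No child is added and N stays at 19. Item 2 needs only dates the trial holds; the diagnosis date is collected at registration (4.2). The delayed-entry estimate will have a wider interval and small early risk sets. It assumes that entry time is unrelated to later survival, and it says nothing about the period before the earliest entry. It does not correct for the exclusion of progressors. Item 3 depends on data that may not exist, and at 70% OS12 it lowers power to 67% at cut-off 13 or 47% at cut-off 14. The stated claim becomes less favourable.
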